3.2 Exclusion Criteria (none of the following may be present for enrollment)

- 3.2.1 Clinical picture indicative of leukostasis or evidence of disseminated intravascular coagulopathy.
- 3.2.2 Uncontrolled coagulopathy or bleeding disorder.
- 3.2.3 Systemic antineoplastic therapy or radiotherapy for other malignant conditions within 14 days before the first dose of any study drug, except for hydroxyurea.
- 3.2.4 Uncontrolled high blood pressure (*i.e.*, systolic blood pressure >180 mm Hg, diastolic blood pressure >95 mm Hg).

- 3.2.5 Female patients who intend to donate eggs (ova) during the course of this study or 4 months after receiving their last dose of study drug(s).
- 3.2.6 Male patients who intend to donate sperm during the course of this study or 4 months after receiving their last dose of study drug(s).
- 3.2.7 Ongoing toxicities \geq grade 2 from prior therapy, except those related to hydroxyurea (which is permitted through the first 5 days of study treatment).
- 3.2.8 APL (M3).
- 3.2.9 Active central nervous system (CNS) leukemia.
- 3.2.10 History of allergic reactions attributed to compounds of similar chemical or biologic composition to MLN4924 (pevonedistat) or belinostat.
- 3.2.11 Stem cell transplant within previous 3 months prior to initiation of study therapy.
- 3.2.12 Major surgical procedures \leq 28 days before beginning study treatment or minor surgical procedures \leq 7 days before beginning study treatment. No waiting required after placement of a vascular access device.
- 3.2.13 Uncontrolled intercurrent illness or infection.
- 3.2.14 Circulating blast count $>50,000 \text{ mm}^3$ within 7 days preceding enrollment.
- 3.2.15 Current candidacy for a potentially curative allogenic stem cell transplant, unless declined.
- 3.2.16 Left ventricular ejection fraction (LVEF) $<50\%$ as assessed by echocardiogram or radionuclide angiography.
- 3.2.17 Prolongation of the heart-rate corrected QT (QTc) interval $\geq 450 \text{ ms}$ (*i.e.*, grade 1 or higher) on electrocardiogram (ECG) prior to initiation of study treatment.
 - If baseline QTc on screening ECG is $\geq 450 \text{ ms}$ (*i.e.*, grade 1 or higher):
 - Check potassium and magnesium serum levels, and
 - Correct any identified hypokalemia and/or hypomagnesemia and repeat ECG to confirm QTc interval.

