6.2 Definition of Dose-Limiting Toxicity

AEs will be assessed according to the NCI Common Terminology Criteria for Adverse Events

(CTCAE), version 5.0. AEs possibly, probably, or definitely related to study drugs will be scored as toxicities.

All participating sites are expected to notify the Principal Investigator and Study Coordinator within 24 hours of awareness that a DLT has occurred.

• [REDACTED]

DLTs will be defined in Cycle 1 as any of the following events that are considered by the investigator to be related to therapy with MLN4924 (pevonedistat) and/or belinostat:

- Any grade 3 or greater non-hematological toxicity that does not recover within 1 week to grade ≤ 1 or baseline with optimal medical management, with the following exception :
 - Grade 3 hypophosphatemia
- Grade 3 or greater ECG QT corrected interval prolonged.
- Grade 3 or greater increased prothrombin time/international normalized ratio (PT/INR) or activated partial thromboplastin time (aPTT) in the absence of anticoagulation therapy.
- Grade 2 or greater elevation of the PT/INR or aPTT that is associated with clinically significant bleeding (CNS, GI, *etc.*).
- Grade 2 or greater increased AST, ALT or bilirubin that persists longer than 2 days between MLN4924 (pevonedistat) doses.
- Delayed initiation of Cycle 2 as follows:
 - More than 2 week delay due to lack of recovery (to $<$ Grade 1 or baseline) from treatment-related non-hematologic toxicity.
 - More than 4 week delay due to lack of recovery (to $<$ Grade 1 or baseline) from treatment-related hematologic toxicity believed not related to leukemic infiltration. Note: Bone marrow evaluation may be required.
- Grade 4 neutropenia or thrombocytopenia extending beyond day 42 in patients with less than 5% blasts in marrow, absence of MDS changes and/or absence of disease by flow cytometry in the marrow.
- Any toxicity that requires discontinuation of either study drug.
- Grade 3 or greater nausea or vomiting despite use of optimal anti-emetic prophylaxis. Optimal anti-emetic prophylaxis is defined as an anti-emetic regimen that employs a 5-hydroxytryptamine 3 serotonin receptor antagonist given in standard doses and according to standard schedules.
- Grade 3 or greater diarrhea that occurs despite maximal supportive therapy
- Grade 3 arthralgia or myalgia despite the use of optimal analgesia

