ECG QTc Interval Prolonged	
If QTc is ≥ 450 ms (i.e., grade 1 or higher):
 
 • Check potassium and magnesium serum levels. • Correct any identified hypokalemia and/or hypomagnesemia and repeat ECG to confirm QTc. 
When HR is between 60-100 bpm, manual measurement of QT interval and use of Fridericia calculation is NOT required.
 
When HR < 60 or > 100 bpm, manual measurement of QT interval by cardiologist is required, with Fridericia correction applied to that manual measurement to determine the QTc.
 
Any questions or concerns about ECG readings will be reviewed with a cardiologist.
 
When concurrent use of MLN4924 (pevonedistat) and/or belinostat with any drug on the Credible Meds list of “drugs with known TdP risk” cannot be avoided, review QTc prior to concurrent use. If pre-concurrent use QTc is:
 
 • Grade 0 (< 450 ms), follow-up QTc evaluation should be done at the next scheduled visit. • Grade 1 (450-480 ms), follow-up QTc evaluation should be done within 8 days after concurrent use starts. • Grade 2 (481-500 ms), withhold MLN4924 (pevonedistat)/belinostat until follow-up ECG at next possible opportunity shows QTc Grade ≤ 1 (≤ 480 ms); evaluate QTc within 8 days after reintroduction of MLN4924 (pevonedistat)/belinostat. 
Any new onset of dysrhythmia on ECG will be reviewed and managed with input from cardiology.
 
For any episode of syncope (grade 3) pre-syncope (grade 2) or QTc grade 3 or 4 (≥ 501ms or > 60 ms change from baseline) or 4 (Torsade de pointes or polymorphic ventricular tachycardia or signs/symptoms of serious arrhythmia), see Section 7.

Gastrointestinal Toxicity	
Gastrointestinal disturbances, including nausea, vomiting and diarrhea, have been reported with belinostat and may require the use of antiemetic and antidiarrheal medications. Fluid and electrolytes should be replaced to prevent dehydration. Pre-existing nausea, vomiting, and diarrhea should be adequately controlled before beginning therapy.

Antiemetic Therapy	
Prophylactic and therapeutic treatment for nausea and vomiting is recommended. The choice of agent is at the discretion of the treating physician. Recommendation to use low-dose dexamethasone, ondansetron (4 mg per dose), or lorazepam. Caution should be exercised when administering ondansetron, palonosetron, or prochlorperazine because of potential QT prolongation risks with belinostat. See above.

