	3	
 Omit belinostat (if only belinostat due); or delay both agents (if both agents due).^{E, F} Check and, as indicated, administer potassium to achieve levels ≥ 4 mmol/L and magnesium to levels ≥ 2 mg/dL; consider chronic oral supplementation of potassium and/or magnesium. Review event and attribution with principal investigator prior to patient's next scheduled treatment, considering the following options: 
 Proceed with belinostat on the same day, if feasible, once QTc ≤ 480 ms and potassium ≥ 4 mmol/L and magnesium ≥ 2 mg/dL; or Omit belinostat (if only belinostat due); or delay both agents (if both agents due) until QTc recovers to ≤ 480 ms ^{E,F} When QTc recovers to ≤ 480 ms, resume belinostat cautiously, with additional QTc monitoring within 3-8 days from reintroduction. If QTc prolongation is thought to be related to belinostat, resume treatment with one dose-reduction step for belinostat. For grade 3 QTc prolongation thought to be related to belinostat that recurs following belinostat dose reduction, discontinue protocol therapy. 	
 Delay both agents. E, F Check and immediately administer potassium to achieve levels ≥ 4 mmol/L and magnesium to levels ≥ 2 mg/dL; consider chronic oral supplementation of potassium and/or magnesium. Review event and attribution with principal investigator prior to patient's next scheduled treatment, considering the following options: 
 Proceed with treatment on the same day, if feasible, once QTc ≤ 480 ms and potassium ≥ 4 mmol/L and magnesium ≥ 2 mg/dL; or Delay both agents until QTc recovers to ≤ 480ms^{E,F} When QTc recovers to ≤ 480 ms, resume MLN4924 (pevonedistat) cautiously, with additional QTc monitoring within 3-8 days from reintroduction. If QTc prolongation is thought to be related to MLN4924 (pevonedistat), resume treatment with one dose-reduction step for MLN4924 (pevonedistat). For grade 3 QTc prolongation thought to be related to MLN4924 (pevonedistat) that recurs following MLN4924 (pevonedistat) dose reduction, discontinue protocol therapy.
	4	Discontinue protocol therapy.	Discontinue protocol therapy.

Toxicity	Grade (CTCAE v5.0)	Modification of Belinostat ^{A, B}	Modification of MLN4924 (pevonedistat) ^{A, B, C}

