																		

- A. MLN4924 (pevonedistat): Dose as assigned; IV over 60 minutes (\pm 10 minutes) once daily (QD) on Days 1, 3, and 5 of each 21-day cycle. When both drugs are given on the same day (Days 1, 3, 5), start the MLN4924 (pevonedistat) infusion within 60 mins after the completion of belinostat infusion.
- B. Belinostat: Dose as assigned; IV over 30 minutes QD on Days 1-5 of each 21-day cycle. Infusion may be extended to 3 hours pending patient tolerance.
- Prior to treatment
 - Unless stated otherwise, baseline evaluations are to be conducted within 1 week prior to start of study therapy. Repeat if not within 1 week prior to Cycle 1, Day 1. In the event that the patient's condition is deteriorating, laboratory evaluations should be repeated within 48 hrs prior to initiation of the next cycle of therapy.
 - End of treatment visit occurs after completion of all study treatment.
 - See Section 6.8.
 - Only for patients with a CR, CRi, CRc, CRm, ML-FS, PR, or SD, capture reported clinical status approximately every 2 months for 2 years following end of safety follow-up until disease progression or death. See Section 6.8.
 - Urinalysis to include turbidity and color, pH, specific gravity, protein, ketones, bilirubin, occult blood, nitrite, glucose, and leukocyte esterase. Microscopic analysis should be done at the discretion of the treating physician.
 - Include over-the-counter medications.
 - Sodium, potassium, carbon dioxide content, chloride, creatinine, blood urea nitrogen (BUN), glucose and calcium.
 - Alkaline phosphatase, ALT, AST and total bilirubin assessments must be performed and read prior to each dose of MLN4924 (pevonedistat).
 - Total bilirubin, direct bilirubin, ALP (alkaline phosphatase), AST, ALT, total protein, albumin.
 - Hepatitis serologies and, if needed, HBV viral load testing are to be done \leq 4 weeks prior to the start of therapy. HBV viral load only necessary if patients are Hepatitis B Ab positive.
 - Pre- & post-treatment on Cycle 1 Day 4 and whenever clinically indicated. Patients with risk factors for QT prolongation including CHF, bradyarrhythmias, electrolyte abnormalities or those on other drugs known to prolong the QT/QTc interval, such as Class Ia and III anti-arrhythmics, should be closely monitored as clinically indicated with ECGs and serum electrolytes (magnesium, potassium) while on study treatment. See Section 6.5.

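### After a grade 3 QTc event, both drugs may be resumed within the cycle while the rise from baseline is still grade 3 (baseline QTc 419 ms or lower)

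*Combined protocol and SAP*

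**What the plan says.** **Grading.** The QTc row of the Supportive Care Guidelines table in Section 6.5 sets grade 3 at a QTc of at least "501ms or > 60 ms change from baseline" and sends the reader to Section 7. Section 6.2 lists "Grade 3 or greater ECG QT corrected interval prolonged" among the DLTs, which count when they occur in Cycle 1 and are considered related.

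**Release.** For a grade 3 event, Section 7.2.2 first holds treatment, sets targets for potassium (at least 4 mmol/L) and magnesium (at least 2 mg/dL), and asks for principal investigator review before the next scheduled treatment. That review considers two options:
- Same-day dosing: "Proceed with belinostat on the same day, if feasible, once QTc" is at or below 480 ms and both electrolytes are on target.
- A hold until QTc is at or below 480 ms.

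Belinostat then restarts when QTc is at or below "480 ms, resume belinostat cautiously, with additional QTc monitoring within 3-8 days from reintroduction". The pevonedistat column has the same limit: "480 ms, resume MLN4924 (pevonedistat) cautiously, with additional QTc monitoring within 3-8 days". A one-step reduction applies if the event is attributed to that drug.

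**Entry and monitoring.** Section 3.2.17 excludes "Prolongation of the heart-rate corrected QT (QTc) interval" of 450 ms or more and gives no lower limit. The scheduled on-treatment ECGs in Section 11 are taken before treatment and "post-treatment on Cycle 1 Day 4 and whenever clinically indicated".

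**The concern.** The event is defined by two limbs and the release by one. A patient whose event is grade 3 only because of the rise can meet the release limit on the ECG that detects it. A patient who goes above 500 ms can be released while the rise alone still makes the event grade 3.

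This is out of step with the rest of the table. The other grade 3 rows that state a recovery criterion set it below grade 3: grade 2 or lower for a first episode of nausea, vomiting or diarrhoea, below grade 2 for fatigue, and grade 1 or tolerable grade 2 for hypophosphataemia and the residual category. QTc is the exception, although a related grade 3 event in Cycle 1 is a DLT.

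At stake is further dosing of both drugs in the same cycle during a toxicity that the protocol itself still grades as 3.

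**Working it through.** The plan gives no figure of its own to reproduce. The check is threshold arithmetic in whole milliseconds, with B the baseline QTc.

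**Inputs**
- Grade 3: QTc ≥ 501, or QTc − B > 60 (Section 6.5).
- Release: QTc ≤ 480 (Section 7.2.2, both drug columns).
- Eligible baseline: B < 450 (Section 3.2.17).

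**Overlap.** Grade 3 by change needs QTc ≥ B + 61. Both conditions can hold together when B + 61 ≤ 480, that is B ≤ 419. The overlap runs from B + 61 to 480, and the largest rise left at a permitted release is 480 − B.

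| Baseline (ms) | Grade 3 by change and releasable (ms) | Largest rise left at release (ms) | Release value if a rise ≤ 60 is also required: min(480, B + 60) |
|---|---|---|---|
| 380 | 441–480 | 100 | 440 |
| 400 | 461–480 | 80 | 460 |
| 410 | 471–480 | 70 | 470 |
| 419 | 480 only | 61 | 479 |
| 420 | none | 60 | 480 |
| 449 | none | 31 | 480 |

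**Two cases at baseline 400**
- On-study 465: the rise is 65, so the event is grade 3, yet 465 ≤ 480 already meets the QTc test.
- Peak above 500, then 480: the rise is still 80, so still grade 3, and release is allowed.

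**Does another rule close the gap?**
- Sections 7.2.1 and 7.3 require recovery to grade 1 or lower (7.3 also accepts baseline or a level agreed with the principal investigator), but only to start a new cycle.
- Section 7.4, on resuming within a cycle, adds only dose spacing and maximum numbers of doses.
- Footnotes E and F to the 7.2.2 table set time limits: Day 12 for dosing and 14 days for resolution.
- DLT status does not by itself bar re-dosing.

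**Timing.** Belinostat alone is due on Day 4, when the scheduled ECGs are taken. Both drugs are due on Day 5. If dosing resumes on Day 4, the repeat QTc falls on Days 4 + 3 to 4 + 8, that is 7 to 12. If it resumes on Day 5, it falls on Days 8 to 13. Either way it comes after the last undelayed dose on Day 5.

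**The case against.** The strongest reply is that 480 ms is the protocol's consistent working limit. Section 6.5 equates 480 ms or less with grade 1 or lower in its concurrent-medication advice, and the pre-syncope row of 7.2.2 equates values above 480 ms with grade 2 or higher. The change limb appears once, in a garbled sentence. But that sentence then describes grade 4 separately ("60 ms change from baseline) or 4 (Torsade de pointes or polymorphic ventricular tachycardia"), so the change limb belongs to grade 3. The 480 ms labels overlook that limb in the same way and offer no reason for dosing during it.

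Re-dosing is also not automatic. Principal investigator review is required, cardiology handles any ECG question, extra ECGs are allowed, and the investigator can stop treatment. All of this stands and lowers the risk. None of it requires the rise to fall, however, and both options listed for the review use 480 ms.

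The proposed test also treats patients unevenly. A patient with baseline 440 and QTc 500 (rise 60) is grade 2 and continues, while one with baseline 380 and QTc 441–449 would be held. But the row already holds treatment for any grade 3 event; the change only makes release consistent with that hold.

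Two points remain as cautions. Manual measurement with Fridericia correction is required only when heart rate is below 60 or above 100 bpm, so baseline and follow-up values may not be fully comparable. The present grading shares this weakness. The timing of the repeat QTc is a secondary matter that the proposed wording does not resolve.

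**Conclusion.** The concern holds. For eligible baselines of 419 ms or lower, Section 7.2.2 allows both drugs to be resumed within a cycle while the QTc event is still grade 3 under Section 6.5. The remaining rise can be 80 ms at baseline 400 and 100 ms at baseline 380. For baselines of 420–449 ms there is no gap. The 419 ms limit is exact in whole milliseconds and rests only on the protocol's own thresholds.

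The exposure is limited to within-cycle dosing, with no dose after Day 12. If the event is judged unrelated, no reduction is required. After a Day 4 finding, only an extra ECG judged clinically indicated could inform the remaining undelayed doses. The documents give neither a baseline QTc distribution nor an event rate, so how many of the maximum 45 patients would be affected cannot be stated. This is a safety gap that should be closed because closing it is cheap; it does not threaten the trial's design.

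**What to change.** In the grade 3 QTc row of Section 7.2.2, in both drug columns, change the QTc test in the same-day option, the delay option and the resumption line to: QTc ≤ 480 ms and change from baseline ≤ 60 ms. Cardiology may prefer a stricter value. Release then follows the last column of the table above and is unchanged for baselines of 420–449 ms.

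The cost is amendment wording in one table row. No scheduled ECG is added, though an affected patient needs a repeat ECG to show release. Some patients with lower baselines will be held longer. Doses not given by Day 12 are omitted, and 14 days without resolution ends therapy. If an event found on Day 4 is judged unrelated and the Day 4 and Day 5 doses are both lost, the patient has 3 of 5 belinostat doses. That is below the 4 of 5 required by Section 9.3.1, so the patient would be replaced for DLT evaluation.

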7.2 Dose Modifications

7.2.1 General Guidelines

- AEs will be identified and graded according to the NCI CTCAE v5.0. AEs that are not study drug-related (*e.g.*, disease-related AEs) do not require dose modification. Dose modification for non-study drug-related AEs is generally discouraged but permitted at investigator discretion.
- *Dose Modification for Hematology Toxicities:* There is no dose-modification for hematologic toxicity; however, in cases of non-disease related myelosuppression and when clinically indicated, dose modification will require discussion with PI.
- Dose reduction steps are shown in Section 7.1. Dose modification instructions for both agents are outlined in Section 7.2. Details regarding initiation of new cycles, resumption of treatment within a cycle and dose re-escalation are shown in Sections 7.3, 7.4 and 7.5, respectively.
- Dose modifications (including dose omission, dose reduction, and delays) will be based on the investigator's assessment of the relationship of the toxicity to each of the study drugs.
 - Belinostat should be modified only for AEs thought to be related to belinostat

- MLN4924 (pevonedistat) should be modified only for AEs thought to be related to MLN4924 (pevonedistat)
- If the AE could be related to both drugs or if the relationship of the AE is unclear, both study drugs should be modified.
- If a patient experiences several AEs and there are conflicting recommendations for dose modification, the investigator should observe the more cautious modification recommendation. Treatment Delays and Omissions:
 - At the beginning of a cycle:
 - All treatment-related toxicities must be resolved to \leq grade 1 for initiation of a new cycle (see Section 7.3).
 - Initiation of a new cycle occurs when both agents meet criteria to be given.
 - Delay in initiation of a new cycle by > 14 days requires discontinuation of study therapy.
 - Within a cycle:
 - **On days when only belinostat is due, if treatment criteria aren't met due to toxicity, then the belinostat dose scheduled on that date will be omitted and not made up** on a later date. When belinostat is omitted, patients should be assessed to determine if dosing may resume on the next scheduled dosing day.

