 - **On days when both study agents are due, if treatment criteria aren't met due to toxicity, for either agent, then both agents will be delayed.** Dosing days will shift accordingly, allowing delayed treatment to resume on a later date in the cycle - with the exception that no dosing may occur after Day 12 of any cycle. Doses not delivered on or before Day 12 will be omitted for that cycle. When treatment is delayed, patients should be evaluated regularly to determine if dosing may resume, with a goal of delivering as much of the regimen as possible on or before Day 12.
- Permanent discontinuation of either study agent requires discontinuation of study treatment.
- Treatment delay of >14 days requires discontinuation of study treatment.

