
A. Refer to the General Guidelines in Section 7.2.1 All treatment related toxicities must be resolved to \leq grade 1 for initiation of a new cycle (see Section 7.3).
 
B. On days when only belinostat is due, if treatment criteria aren't met due to toxicity, the belinostat dose scheduled on that date will be omitted and not made up on a later date, with assessment to resume treatment done on the next scheduled dosing day. On days when both study agents are due, if treatment criteria aren't met for both agents, then both agents will be delayed and the schedule shifted to accommodate for the delay. Assessment to resume treatment will be done regularly to determine if dosing may resume, with a goal of delivering as much of the regimen as possible on or before Day 12.
 
C. For MLN4924 (pevonedistat), a minimum of 1 full calendar day between any 2 doses should be maintained, and a maximum of 3 doses of MLN4924 (pevonedistat) within the cycle must not be exceeded.
 
D. There are no dose modifications for grade 1 toxicity. For grade 2 toxicity, the dose of the study drug(s) may be reduced by one dose-reduction step at the investigator's discretion.
 
E. Within a cycle, if treatment is delayed, treatment must be resumed no later than Day 12; and all dosing for a cycle must be completed on or before Day 12.
 
F. If toxicity has not resolved after 14 days of treatment delay, protocol therapy will be discontinued.
 
G. Dose modifications are not required for asymptomatic laboratory abnormalities (other than increased AST, ALT, and bilirubin, for which dose modifications are listed on the table above).
			

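### After grade 3 QTc prolongation, the one ECG required after re-exposure can fall entirely on non-dosing days when treatment resumes on Day 4, Day 5 or a shifted Day 5

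*Combined protocol and SAP*

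**What the plan says.** The grade 3 row for prolonged QTc in section 7.2.2 holds treatment until QTc is 480 ms or lower. It also sets potassium and magnesium targets, requires review with the principal investigator before the next scheduled treatment, and reduces the dose of a drug thought responsible. After that, the belinostat column says to "resume belinostat cautiously, with additional QTc monitoring within 3-8 days from reintroduction" and the pevonedistat column to "resume MLN4924 (pevonedistat) cautiously, with additional QTc monitoring within 3-8 days from reintroduction". Neither column ties the ECG to a dosing day or to a time after infusion.

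The stopping rule for belinostat-related grade 3 prolongation reads "that recurs following belinostat dose reduction, discontinue protocol therapy". The pevonedistat column has a matching rule.

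Section 7.2.1 governs missed doses. On a belinostat-only day when criteria are not met, "then the belinostat dose scheduled on that date will be omitted and not made up". Days on which both drugs are due are shifted instead, "with the exception that no dosing may occur after Day 12 of any cycle". Footnote E to the section 7.2.2 table repeats the limit: "all dosing for a cycle must be completed on or before Day 12".

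Outside that row, the ECG footnote of the Study Calendar (section 11) sets the only scheduled on-treatment ECG: "Pre- & post-treatment on Cycle 1 Day 4 and whenever clinically indicated". Patients with QT risk factors "should be closely monitored as clinically indicated with ECGs and serum electrolytes".

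**The concern.** Dosing occupies the first five days of a 21-day cycle, and the ECG window opens about three days after the drug is restarted. When the restart comes late in the dosing week, dosing can be over before the window opens. A normal tracing would then satisfy the row without showing what the re-challenge dose did to QTc.

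This matters because the stopping rule in the same row depends on recurrence being seen, in a patient who has already had a grade 3 QTc event. The row's other safeguards act before or at resumption. Earlier ECGs are permitted, but their timing is left to judgement. What is at stake is patient safety and the recording of recurrence.

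The point is stronger for belinostat, whose risk list (section 10.1.1.2) names QTc prolongation. The pevonedistat list (section 10.1.1.1) does not.

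**Working it through.** This is a count of calendar days; the plan gives no figure to reproduce.

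**Inputs.** Dosing days: belinostat 1-5, pevonedistat 1, 3 and 5 (sections 6.1 and 11). Window: 3-8 days from reintroduction (section 7.2.2). Last permitted dosing day: Day 12 (section 7.2.1). Next cycle: Day 22 at the earliest, since cycles last 21 days.

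**Formula.** For resumption on day d, the window is [d+3, d+8] if days are counted as elapsed, or [d+2, d+7] if reintroduction is day 1. The plan does not say which, so both are shown. Count the remaining dosing days of the reintroduced drug inside the window, assuming no other hold in that cycle.

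| Resume on | Window, elapsed | Window, inclusive | Belinostat dosing days inside (elapsed / inclusive) | Pevonedistat dosing days inside (elapsed / inclusive) |
|---|---|---|---|---|
| Day 1 | 4-9 | 3-8 | 2 / 3 | 1 / 2 |
| Day 2 | 5-10 | 4-9 | 1 / 2 | not given |
| Day 3 | 6-11 | 5-10 | 0 / 1 | 0 / 1 |
| Day 4 | 7-12 | 6-11 | 0 / 0 | not given |
| Day 5 | 8-13 | 7-12 | 0 / 0 | 0 / 0 |
| Day 5 shifted to Day 6 | 9-14 | 8-13 | 0 / 0 | 0 / 0 |
| Day 5 shifted to Day 12 | 15-20 | 14-19 | 0 / 0 | 0 / 0 |

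Shifts to Days 7-11 lie between the last two rows and also give 0 / 0. Every window ends by Day 20, before the next cycle.

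**Distance from the last resumed dose to the window (elapsed / inclusive).**
- Resume Day 4, last dose Day 5: start 7-5 = 2 / 6-5 = 1 days; end 12-5 = 7 / 11-5 = 6 days.
- Resume Day 5, last dose Day 5: start 8-5 = 3 / 7-5 = 2 days; end 13-5 = 8 / 12-5 = 7 days. A shifted Day 5 gives the same distances.

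**Link to the scheduled ECG.** Suppose the grade 3 finding comes from the Cycle 1 Day 4 ECG and the cycle has had no earlier hold. Same-cycle resumption is then possible on Days 4-12 for belinostat (12-4+1 = 9 days) and Days 5-12 for pevonedistat (12-5+1 = 8 days). With no further hold, none of these has a dosing day in the window.

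**Where the no-other-hold condition matters.**
- Earlier hold: if a planned Day 3 has already slipped to calendar Day 5, belinostat falls on Days 5, 6 and 7. The inclusive window for d = 5 is Days 7-12 and contains Day 7; the elapsed window, Days 8-13, contains none.
- Further hold: if belinostat resumes on Day 4 and the Day 5 dose is then delayed to Days 7-12, that dose falls inside the elapsed window.

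**The case against.** The strongest reply is that harm is not shown. It requires prolongation that appears on dosing and has gone by the time of the ECG. The documents give no QTc time course for either drug, and the pevonedistat QTc study in section 2.2.2.2 is named without results. A reader might infer from belinostat's half-life of 0.3 to 1.3 hours (section 2.2.1.2) that any effect has passed, since 24 / 1.3 is about 18 half-lives after one day. That describes clearance of the drug, not duration of the QTc effect. If prolongation is delayed or persistent, the present window is the better check. This objection stands, and it is why the later ECG should not be replaced.

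Second, the window fits the Cycle 1 visit schedule. By the elapsed count, Day 4 and Day 5 resumptions include the Day 8 visit, and shifts to Days 7-12 include the Day 15 visit, both with a metabolic panel and magnesium. Only a shift to Day 6 misses both. This is coherent, though the plan does not give it as the reason, and it supports keeping the later check rather than omitting an on-dose one.

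Third, a reader might infer that these patients go unmonitored on drug. The documents do not support that. The row calls for caution and for monitoring that is additional, the risk-factor list in the calendar footnote is open-ended, and syncope or pre-syncope triggers an ECG. A same-day resumption on Cycle 1 Day 4 already has a post-treatment ECG that day, although not on the Day 5 dose that follows. What remains uncovered is an asymptomatic, transient recurrence in a patient for whom nobody ordered an earlier ECG.

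**Conclusion.** The point holds as a limited gap in the monitoring rule. For a planned Day 4 (belinostat), planned Day 5, or planned Day 5 shifted to Days 6-12, with no earlier or further hold in the cycle, the required window contains no dosing day under either count. For a planned Day 3 this is true only by the elapsed count. Day 1 and Day 2 resumptions are not affected. No section requires an ECG on the Day 5 or shifted Day 5 re-challenge dose. The plan's own scheduled ECG is taken before and after treatment, which suggests that it regards on-dose readings as informative.

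Two broader readings should be resisted. One is that no same-cycle resumption after a Cycle 1 Day 4 finding can ever have a dosing day in the window; the earlier-hold example shows that it can. The other is that the DLT count, and so dose selection, is affected. It is not: section 6.2 already makes a treatment-related grade 3 QTc event in Cycle 1 a DLT, and only Cycle 1 DLTs influence escalation.

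The size is in calendar days, not in patients or probabilities. Recurrence on dosing is inferred and its frequency is unknown. For pevonedistat, off-drug here means only that no dose is given that day, because the documents report no half-life for it. Severity: could be changed; a cheap improvement.

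**What to change.** Amend both columns of the grade 3 QTc row:
- When the 3-8 day window includes a dosing day of the reintroduced drug, take the ECG post-dose on such a day.
- When it includes none, take a post-dose ECG after the last resumed dose of that cycle (the first, if it is the only one). Keep the 3-8 day ECG as the check for delayed or persistent prolongation.

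With unshifted dosing, resumptions on Days 3, 4 and 5 then all yield a post-dose Day 5 ECG under either count. A shifted Day 5 yields an ECG after that dose.

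The cost is one additional ECG at an infusion visit that is already scheduled, only for patients who resume late after a grade 3 QTc event. For early resumptions no ECG is added, but the usable days narrow to the one to three dosing days inside the window.
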